## **9.6. Vital Signs**

Vital signs parameters will be summarized by means of descriptive statistics at each analysis visit. Actual values and changes from baseline will be tabulated separately.

All vital signs data will be listed.

## **9.7. Physical Examination**

Clinically significant abnormalities detected during the baseline physical examinations will be recorded and presented as Medical History.

Clinically significant abnormalities detected during post-baseline physical examinations will be recorded and presented as Adverse Events.

## **9.8. ECGs**

Descriptive statistics (mean, standard deviation) will be presented for all mean parameter values for the triplicate ECG parameters at every visit. Listings for change from baseline and all ECGs with abnormal interpretation will be created.

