## LIST OF ABBREVIATIONS

Term	Definition
AE(s)	Adverse event(s)
ALT	Alanine aminotransferase
APRI	Aspartate aminotransferase-to-platelet ratio index
AST	Aspartate aminotransferase
AUC	Area under the plasma concentration-time curve
AUC t	area under the plasma concentration-time curve from time 0 to the last time point (ie, corresponding to a quantifiable concentration)
BEM	Bemnifosbuvir
BMI	Body mass index
CI(s)	Confidence interval(s)
C max	Maximum observed plasma concentration
COVID-19	Coronavirus Disease 2019
CRO	Contract research organization
DAA(s)	Direct acting antiviral(a)
DAIDS	Division of AIDS
DDI	Drug-drug interaction
EC 50/95	50% effective concentration
ECG	Electrocardiogram(s)
eCRF	Electronic case report form
EDC	Electronic Data Capture
E max	Maximal effect
EOS	End of Study, defined as the day in which the subject completes their last assessment; the planned EOS is study Week 32 (i.e., 24 weeks posttreatment)
EOT	End of Treatment, defined as the last day study drug is administered; the planned EOT is at the end of Week 8
ET	Early termination
EU	European Union
FDC	Fixed-dose combination
GCP	Good Clinical Practices
(e)GFR	(Estimated) Glomerular filtration rate
GT	Genotype
HbA 1c	Hemoglobin A 1c
HBsAg	Hepatitis B surface antigen
HBV	Hepatitis B virus
HCC	Hepatocellular carcinoma
HCV	Hepatitis C virus
HIV	Human immunodeficiency virus

ICF	Informed consent form
ICH	International Conference on Harmonisation
IEC	Independent Ethics Committee
IMP	Investigational Medicinal Product
INR	International Normalized Ratio
IRB	Institutional Review Board
LLOQ	(Lower) Limit of quantitation
MDRD	Modification of Diet in Renal Disease
MedDRA	Medical dictionary for regulatory activities
NS	Nonstructural
NS5A	Nonstructural protein 5A
NS5B	Nonstructural protein 5B
PD	Pharmacodynamic
P-gp	P-glycoprotein
PK	Pharmacokinetic(s)
PP	Per protocol
PT	Preferred term / Prothrombin time
QTcF	Fridericia-corrected QT interval
RAV(s)	Resistance-associated variant(s)
RBC	Red blood cell
RZR	Ruzasvir
SAE(s)	Serious adverse event(s)
SAP	Statistical analysis plan
SVR4/12/24	Sustained virologic response at 4/12/24 weeks posttreatment
ULN	Upper limit normal
UPR	uprifosbuvir
VK	Viral kinetics

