a Screening window may be extended to 42 days for extenuating circumstances with Sponsor approval.

b Day 1 assessments performed prior to dosing.

c The last dose is on Day 56. The last visit of the treatment period shall occur no sooner than Day 57 and no later than Day 60 (inclusive).

d Three consecutive determinations collected, with no less than 1 minute between individual ECGs. Complete ECGs prior to any blood draws.

e For females of childbearing potential, serum or urine is acceptable.

f Plasma samples collected for resistance testing. At least one baseline resistance sample is needed (Screening and/or Day 1 predose); there is no protocol deviation if there is one evaluable baseline sample for resistance testing. In addition, the resistance sample is not required for screening and eligibility purposes.

g On Day 1, the PK sample will be obtained predose. The sampling time and time of last dose must be recorded.

h See Table 3

i Subjects may be contacted between visits to assess compliance, concomitant medications, and AEs/SAEs.

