## **7. ADVERSE EVENTS**

### **7.1. Definitions**

An AE is defined as any untoward medical occurrence in a subject administered a medicinal product(s) and which does not necessarily have to have a causal relationship with this treatment. An AE can therefore be any unfavorable and unintended sign (for example, an abnormal laboratory finding), symptom, or disease temporally associated with the use of a medicinal product(s), whether or not considered related to this medicinal product(s). The worsening of a pre-existing condition (i.e., clinically significant change in frequency and/or intensity) that occurs during study participation is also an AE.

A suspected adverse reaction is any AE for which there is a reasonable possibility that the drug(s) caused the AE. ‘Reasonable possibility’ means there is evidence to suggest a causal relationship between the drug(s) and the AE. A suspected adverse reaction implies a lesser degree of certainty about causality than adverse reaction, which means any AE caused by a drug(s).

An AE may be:

- A new illness
- Worsening of a concomitant illness
- An effect of the study medication(s); it could be an abnormal laboratory value as well as a significant shift from baseline within normal range which the qualified investigator or medically qualified designate considers to be clinically significant

Symptoms or conditions reported prior to consent are not AEs; these will be recorded as part of medical history.

Surgical procedures themselves are not AEs. They are therapeutic measures for conditions that required surgery. The condition for which the surgery is required is an AE, if it occurs/, or worsens during the study period. Planned (elective) surgical measures and the conditions(s) leading to these measures are not AEs, if the condition(s) existed or was (were) known before the time of informed consent. In the latter case, the condition should be reported as medical history.

An SAE or reaction is any untoward medical occurrence that at any dose:

- Results in death
- Is life-threatening
- Requires inpatient hospitalization or prolongation of existing hospitalization
- Results in persistent or significant disability or incapacity (defined as a substantial disruption of a person’s ability to conduct normal life functions)
- Is a congenital anomaly or birth defect

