## 8.5. Safety Analyses

Study treatment exposure (such as treatment duration and total dose received) will be summarized with descriptive statistics.

Treatment-emergent AEs and graded laboratory abnormalities, defined as any new or worsening AE/laboratory parameter beginning on or after the first dose of study drugs through 4 weeks after the last dose, will be included in the analysis.

Incidence and frequency of subjects experiencing AEs, SAEs, AEs resulting in treatment discontinuation, and AEs resulting in study discontinuation will also be summarized. Adverse events will be coded using MedDRA. The incidence and frequency of subjects with treatment-emergent adverse events will be tabulated by primary SOC and PT. The tabulation of the number of subjects with treatment-emergent AEs will also be provided by grade and relationship to study drug.

Changes from baseline in laboratory tests and vital signs will be summarized. Laboratory abnormalities will be graded in accordance with the DAIDS severity scale where applicable. Shift tables for treatment-emergent laboratory abnormalities will be presented.

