## **6. GENERAL CONSIDERATIONS FOR DATA ANALYSES AND HANDLING**

### **6.1. General Summary Table and Individual Subject Data Listing Considerations**

Unless otherwise specified, continuous variables will be summarized by using the number of non-missing observations, arithmetic mean, standard deviation (SD), minimum, first quartile, median, third quartile and maximum values as summary statistics; categorical variables will be summarized by using the frequency count and the percentage of subjects in each category as summary statistics.

When a summary tabulates the number of subjects, subjects will only be counted once for a category (e.g., a particular adverse event type, a particular adverse event term, a particular concomitant medication) unless otherwise specified.

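### SAP 9.8 plans no table of within-subject QTcF change or of the number of subjects with a QTcF rise; adding both before database lock would cost little

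*SAP*

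**What the plan says.** SAP 9.8 has two sentences on ECGs. The first sets the table: "Descriptive statistics (mean, standard deviation) will be presented for all mean parameter values for the triplicate ECG parameters at every visit". The second sets the listings: "Listings for change from baseline and all ECGs with abnormal interpretation will be created".

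The neighbouring safety sections go further. SAP 9.6, on vital signs, states: "Actual values and changes from baseline will be tabulated separately". SAP 9.5 has the same rule for laboratory data and adds counts of treatment-emergent toxicity grades and baseline-to-worst shift tables.

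Protocol 8.2.4 names ECG parameters as a safety endpoint, and safety is a primary objective (Protocol 2.1). On change, Protocol 8.5 says only: "Changes from baseline in laboratory tests and vital signs will be summarized". ECG is not in that sentence.

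The only QTcF limits in either document are the entry limits in Protocol 4.2: 440 ms for males and 460 ms for females.

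**The concern.** Of the three measured safety domains, ECG is the only one with no table of change. A table of visit means and SDs says nothing about the spread of within-subject change, and it can hide a few large rises. The listings show individual cases, but the report would contain no pre-specified rate of QTcF prolongation. Anyone who later counted from the listings would have to choose the cut-offs and the time window at that point, in an open-label trial with the data in view. Fixing them before lock limits that freedom without removing it. SVR12 and the sample size are not affected.

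**Working it through.** The plan gives no figure to reproduce. The steps below show what the planned table can and cannot reveal, and how a count would behave.

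**Inputs.** N = 280 is planned enrolment (Protocol 3.2), taking every subject as having the ECG. ECGs fall at Screening, Baseline, Week 4, Week 8, ET and Follow-up Week 4 (Protocol Table 2). The SDs, correlations and the 30 and 60 ms cuts are assumptions; the documents give none of them.

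**1. A few large rises in a visit table.** Let 3 subjects rise by 60 ms, with a visit SD of 20 ms.
- Shift in the mean: 3 × 60 / 280 = 0.64 ms.
- Standard error of the mean: 20 / √280 = 1.20 ms, so the shift is about half a standard error.
- New visit SD: √(20² + (3/280)(277/280) × 60²) = 20.9 ms, against 20.0.
- As a count: 3/280 = 1.1%, Wilson 95% CI 0.4% to 3.1%.

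The table would barely move, whereas a count states the event directly.

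**2. Same visit table, different changes.** With an SD of 20 ms at both visits and no mean change, the SD of change is √(2 × 20² × (1 − r)), where r is the within-subject correlation. The expected number above 30 ms is 280 × [1 − Φ(30 / SD of change)].

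| r | SD of change (ms) | Expected above 30 ms, of 280 |
|---|---|---|
| 0.5 | 20.0 | 18.7 |
| 0.7 | 15.5 | 7.4 |
| 0.9 | 8.9 | 0.1 |

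The visit means and SDs are identical in all three rows, so the number of risers cannot be recovered from them.

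**3. Chance counts with no drug effect.** Give each ECG an independent normal error with within-subject SD s. For k post-baseline ECGs, P(maximum rise > c) = ∫ [1 − Φ((c + x)/s)^k] φ(x/s)/s dx. Multiply by 280. With k = 2 (Week 4 and Week 8):

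| s (ms) | Above 30 ms | Above 60 ms |
|---|---|---|
| 6 | 0.1 | < 0.001 |
| 8 | 2.1 | < 0.001 |
| 10 | 8.7 | 0.006 |
| 14 | 31 | 0.66 |

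The last row is not extreme: a visit SD of 20 ms with r = 0.5 implies s = 20 × √0.5 = 14.1 ms.

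**4. Adding Follow-up Week 4 (k = 3).** For s = 6, 8 and 10 ms the count above 30 ms becomes 0.17, 3.08 and 12.22, against 0.11, 2.14 and 8.74. That is 48%, 44% and 40% more chance counts, from an ECG taken off drug.

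**5. Which ECGs are on drug.** The last dose is on Day 56, and footnote c of Protocol Table 2 puts the Week 8 visit at Day 57 to 60. A completer's only scheduled post-baseline ECG during dosing is therefore Week 4. The protocol's abbreviation list gives EOT as "End of Treatment, defined as the last day study drug is administered", and SAP Table 4 runs the Week 8 window to EOT+20. An ECG assigned to Week 8 could thus be up to 20 days off drug.

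**The case against.** The case for leaving SAP 9.8 alone is respectable. The protocol promises no ECG change table, the trial is single-arm and descriptive with no tests (SAP 8.1, 8.3, 8.4), and every subject's change from baseline and every abnormal ECG will be listed. Neither drug has a reported earlier ECG signal (Protocol 1.4 for BEM, 1.2.2 for RZR). No stopping rule in Protocol 5.6 uses QTcF, so no trial decision depends on a count. ECG abnormalities with signs or symptoms must be recorded as AEs when they meet the definition (Protocol 7.1), and the AE tables then count them. All of this stands, and it keeps the point minor.

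It does not fill the gap. The fuller summary in SAP 6.1 ("arithmetic mean, standard deviation (SD), minimum, first quartile, median, third quartile and maximum values as summary statistics") applies unless otherwise specified, and 9.8 specifies mean and SD. Even the full set, on actual values, gives neither change nor threshold counts. The AE definition is broad enough to take in an asymptomatic rise ("An AE can therefore be any unfavorable and unintended sign (for example, an abnormal laboratory finding), symptom, or disease"), but reporting one rests on the investigator's judgement.

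Three objections to the count itself also stand. The row above 30 ms is hard to read without a control arm. Two scheduled ECGs, one of them after dosing has ended, are thin evidence. And a count ending near the last dose departs from the first-dose-to-4-weeks window that Protocol 8.5 uses for AEs and graded laboratory results and SAP 9.1 uses for AEs, so the SAP should say so.

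**Conclusion.** This is a cheap improvement. The planned tables show neither within-subject QTcF change nor the number of subjects with a rise, and visit means would not show a handful of large ones (0.64 ms for 3 of 280 at +60 ms, against a standard error of 1.2 ms at an assumed SD of 20 ms).

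A reader might infer three stronger things that the documents do not support:
- **That the SAP falls short of the protocol.** Protocol 8.5 limits its promise of change summaries to laboratory tests and vital signs.
- **That a QT problem is being obscured.** No earlier signal is reported, and the individual data are listed.
- **That a clean count would settle the matter.** The Wilson upper limit for 0/280 is 1.4%, but it bounds only prolongation visible at the scheduled ECGs, so it is weak reassurance.

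For assumed within-subject SDs of 6 to 14 ms, chance alone gives 0.1 to 31 of 280 above 30 ms and about 0 to 0.7 above 60 ms. The higher cut is therefore the more readable one, though it is not free of chance counts at the larger SDs.

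**What to change.** Replace the first sentence of SAP 9.8 with text to this effect:

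*For each ECG parameter (mean of the triplicate), the Section 6.1 statistics will be given at each analysis visit, in separate tables for observed values and for change from baseline. Number (%) of subjects will be given by maximum post-baseline increase in QTcF (> 30 to 60 ms, > 60 ms) and by maximum post-baseline QTcF (> 480 to 500 ms, > 500 ms). These counts use all ECGs after the first dose through the Week 8 or ET visit, including every ET ECG, with days since last dose stated. Follow-up Week 4 is shown separately. This window differs from the 4-week treatment-emergent window used for AEs and laboratory data.*

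Keep the listings. The four cut-offs are examples, since the documents set no post-baseline limit. The sponsor may choose others, provided they stand in the SAP as numbers before database lock. Keeping every ET ECG matters because Protocol 5.7 sets no time limit for that visit, and a short cut-off after the last dose could drop early stoppers, including those who stopped for an AE.

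The cost is one paragraph and one or two tables from ECGs already collected. The report should note the missing control arm, the few ECGs not timed to dosing, and the second time window.

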## **9.9. Study Termination Status**

The following subject data will be tabulated:

- The number and percentage of subjects who completed or discontinued the study and the number and percentage of subjects for each study discontinuation reason
- The number and percentage of subjects who completed or discontinued the study drug and the number and percentage of subjects for study drug discontinuation reason including Adverse Events leading to study drug discontinuation.

## **10. PHARMACOKINETICS**

### **10.1. Sparse PK analysis**

Sparse PK concentrations will be listed by visit for all subjects with available data.

### **10.2. Serial PK sub-study**

The analysis of the Serial PK sub-study will be discussed in a separate document.

### **10.3. Serial PK/VK sub-study**

The analysis of the Serial PK/VK sub-study will be discussed in a separate document.

## **11. APPENDICES**

### **11.1. Appendix 1**

AT-01B-004 NGS Data Transfer Programming Logic and Table Shells V2.0 20241210

### **11.2. Appendix 2**

AT-01B-004 SAP APPENDIX 2 - Rescue Medications List v1.0 20241028
